7.1 DLT Analysis Set

The DLT analysis set will include DLT-evaluable subjects enrolled in phase 1b who have had the opportunity to be on treatment for at least 6 weeks from the initial dosing of pembrolizumab and received at least 2 doses of talimogene laherparepvec and 2 doses of pembrolizumab in combination (ie, on the same day) or those who otherwise experience a DLT within 6 weeks after starting the combination therapy.

7.2 Full Analysis Set (FAS)

The primary analysis of all efficacy endpoints for phase 3 part of the study, unless noted otherwise, will be conducted on the full analysis set defined as all randomized subjects. All subjects will be analyzed according to treatment to which they are randomized.

7.3 Safety Analysis Set

The safety analysis set will include all subjects who received at least 1 dose of talimogene laherparepvec (or placebo in phase 3) or pembrolizumab. The safety analysis set will be defined separately for the phase 1b and phase 3. All subjects will be analyzed according to the treatment they received. Subjects will be classified in the talimogene laherparepvec and pembrolizumab arm for safety analyses if they received at least one dose of talimogene laherparepvec at any time during the treatment period.

7.4 PD-L1 Negative Analysis Set

The PD-L1 negative analysis set will include all subjects that are PD-L1 negative prior to randomization (phase 3) /first IP dose (phase 1b).

7.5 PD-L1 Positive Analysis Set

The PD-L1 positive analysis set will include all subjects that are PD-L1 positive prior to randomization (phase 3) /first IP dose (phase 1b).

7.6 qPCR Suspicious Lesion Swab Analysis Set

The qPCR Suspicious Lesion Swab Analysis Set will include subjects who are enrolled (phase 1b) or in the FAS (phase 3), receive at least one dose of talimogene laherparepvec / placebo, and have at least one swab sample evaluable result from lesions suspicious to be herpetic in origin during the study. Evaluable samples are sample with either positive, below quantification limit (BQL), or not detected results.

7.7 Per Protocol Analysis Set

The Per Protocol Analysis Set is a subset of the Full Analysis Set (phase 3) which includes subjects who do not have important protocol deviations (IPDs) that are considered to have an impact on efficacy outcomes.

Subjects with any of the following eligibility criteria IPDs will be removed from the Per-Protocol Analysis Set:

- Subject does not have histologically confirmed diagnosis of melanoma
- Subject does not have unresectable stage IIIB, IIIC, IVM1a, IVM1b, or IVM1c melanoma
- Subject is not a candidate for intralesional therapy

Additionally, subjects assigned to the talimogene laherparepvec arm, but who did not receive the first two consecutive doses of talimogene laherparepvec, will be excluded from the Per Protocol Analysis Set

For purposes of the Per-Protocol sensitivity analyses, subjects who (a) received the investigational product not matching the subject's randomized treatment group, or (b) have been identified to have an IPD under the category of prohibited concomitant medications during treatment, all event data collected after the first occurrence of the violation will be excluded from the analysis, and the endpoints analyzed as time-to-event will be censored at the time of the first violation for subjects who have not had an event prior to the violation date.

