3.1.1 Phase 1b

Phase 1b is an open-label, multicenter, single-arm study to evaluate the safety of talimogene laherparepvec in combination with pembrolizumab. Two doses (5 weeks) of talimogene laherparepvec will be administered first prior to addition of pembrolizumab to

approximately 20 subjects with previously untreated, unresectable, stage IIIB to IVM1c melanoma until disappearance of injectable lesions, CR, confirmed PD per modified immune-related Response Criteria (irRC; [Wolchok et al, 2009](#); protocol Appendix D), intolerance of study treatment, 24 months from the date of the first dose of pembrolizumab, or end of study, whichever occurs first. In addition, phase 1b will evaluate potential blood and [REDACTED] that associate with response or resistance to talimogene laherparepvec in combination with pembrolizumab.

The DLRT was to initially meet when 6 subjects are evaluable for DLT. The DLRT was to declare the combination of talimogene laherparepvec and pembrolizumab tolerable if the incidence of DLT is < 33% during the DLT evaluation period. Refer to protocol section 3.1.1.1. for more details.

3.1.2 Phase 3

The phase 3 is a double-blind, placebo-controlled, multicenter randomized trial to evaluate the efficacy, as assessed by PFS and OS of talimogene laherparepvec with pembrolizumab versus placebo with pembrolizumab in subjects with unresectable, stage IIIB to IVM1c melanoma.

Approximately 660 subjects will be randomized 1:1 to receive the following:

- Arm 1: talimogene laherparepvec plus pembrolizumab
- Arm 2: placebo plus pembrolizumab

Randomization will be stratified by stage of disease: less advanced stages (IIIB, IIIC, and IVM1a) versus more advanced stages (IVM1b and IVM1c) and by prior serine/threonine protein kinase B-Raf (BRAF) inhibitor therapy: no prior BRAF inhibitor versus prior BRAF inhibitor with or without MEK inhibitor.

Talimogene laherparepvec/placebo and pembrolizumab treatment will be initiated simultaneously.

Talimogene laherparepvec/placebo will be administered until disappearance of injectable lesions, iCR, documented confirmed progressive disease (iPD) per modified irRC-RECIST (protocol Appendix F), intolerance of study treatment, 24 months from the date of the first dose of talimogene laherparepvec/placebo, or end of study, whichever occurs first.

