9.4 Detection of Bias

Lack of protocol compliance may introduce potential bias in the estimation of protocol endpoints. All important protocol deviations (IPDs) will be reported, documented and stored in eClinical (a clinical trial management system). IPD reports will be produced [REDACTED] by the study manager and will be regularly reviewed in the study team's IPD review meetings as well as before analysis.

Protocol compliance will be examined by tabulating subjects with IPDs. Bias will be evaluated, in part, by conducting sensitivity analyses using the Per Protocol Analysis Set (see [Section 7.7](#)).

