10.5.4 Sensitivity Analyses

[figure not shown]
Sensitivity analyses will be performed for the Phase 3 portion of the study utilizing the Full Analysis Set to assess the robustness of select primary and secondary endpoints as noted below. Primary analysis method for primary efficacy endpoints as well as the secondary efficacy endpoints will be repeated for the Per Protocol Analysis Set to assess the impact of IPDs. All p-values will be descriptive.

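### The Per Protocol set drops subjects who missed either of the first two injections from the talimogene laherparepvec arm only, which is likely to tilt the sensitivity analysis towards treatment

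*SAP*

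**What the plan says.** SAP Section 7.7 builds the Per Protocol set from the Full Analysis Set. Its eligibility rule covers both arms: "Subjects with any of the following eligibility criteria IPDs will be removed from the Per-Protocol Analysis Set". So do its censoring rules for receipt of the wrong product and for prohibited medication. The dose rule does not: "subjects assigned to the talimogene laherparepvec arm, but who did not receive the first two consecutive doses of talimogene laherparepvec, will be excluded". No section of the SAP or protocol adds a placebo counterpart. Where the SAP means both products it says so, as in the Safety Analysis Set (7.3) and the lesion swab set (7.6).

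SAP Section 10.5.4 sets out the use of the set: "Primary analysis method for primary efficacy endpoints as well as the secondary efficacy endpoints will be repeated for the Per Protocol Analysis Set". It adds "All p-values will be descriptive". SAP Section 9.4 gives the purpose: "Bias will be evaluated, in part, by conducting sensitivity analyses using the Per Protocol Analysis Set". The primary analysis itself "will be conducted on the full analysis set defined as all randomized subjects" (SAP Section 7.2).

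**The concern.** The control arm is also injected. SAP Section 3.1.2 reads "The phase 3 is a double-blind, placebo-controlled, multicenter randomized trial", and protocol Table 6 schedules the first two injections at week 0 and week 3 for both products. The same dosing data therefore exist in both arms, and the design gives no reason to treat them differently.

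Whether a subject receives the second injection is known only after randomization. Someone who dies, deteriorates or has an early toxicity before week 3 will miss it. Under protocol Section 6.2.1.2, injections are held for certain toxicities and for corticosteroids above a set level, and an injection delayed long enough counts as missed. OS and PFS start at randomization, so the rule gives the talimogene laherparepvec arm a short immortal period that the placebo arm lacks.

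Response rates are affected too. Subjects with no post-baseline tumor assessment count as non-responders (SAP Section 6), and the rule removes some of them from one arm's denominator only.

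Section 10.5.4 says the analyses are repeated on this set for the purpose of judging protocol deviations: "will be repeated for the Per Protocol Analysis Set to assess the impact of IPDs". An injection missed through death, or through a hold that the protocol requires, is not a deviation. At stake is how the result is read: a Per Protocol hazard ratio at or below the Full Analysis Set value would pass as robustness when part of it comes from how the set was defined.

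**Working it through.** The plan gives no figure for the Per Protocol set, so the design figures were reproduced first to confirm that the survival assumptions were read correctly.

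**Design figures (protocol Section 10.2.2 and Table 12)**
- PFS events: 4 × (2.807 + 1.282)² / (ln 2/3)² = 66.87 / 0.1644 = 407, as stated.
- OS: 340 events in a fixed design at two-sided 0.045 and 90% power. Simulated power at 252, 282, 315 and 346 events with the tabulated nominal levels is 66%, 76%, 84% and 90%, with overall alpha 0.0449. This matches Table 12.

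**Deaths before the second injection is due**
- Three weeks = 21 / 30.4375 = 0.690 months. Control hazard = ln 2 / 28 = 0.02476 per month.
- 1 − exp(−0.02476 × 0.690) = 0.0169, and 0.0169 × 330 = 5.6 subjects per arm.

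**Simulated bias on OS**
- From the protocol: 330 per arm; control OS of 0.50, 0.31 and 0.27 at 28, 48 and 60 months; 26 months of accrual with half enrolled at two thirds of the period; 5% annual loss; cutoff at month 75.
- Method: Cox model with Wald test, 1,500 trials per scenario. Monte Carlo error is about 0.2% to 0.4% on the hazard ratio and 0.4 to 1.1 points on the rates.
- Assumed: the fraction of subjects who miss a dose besides early deaths, and their hazard relative to the rest, the same in both arms.

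Results with no true effect. A false favourable result is p < 0.05 in the direction of talimogene laherparepvec (nominal 2.5%).

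| Further subjects missing a dose | Relative hazard | HR, one-arm rule | False favourable | HR, rule in both arms | False favourable |
|---|---|---|---|---|---|
| none (early deaths only) | – | 0.976 | 5.1% | 0.997 | 2.6% |
| 2% | 4 | 0.957 | 5.9% | 1.004 | 1.9% |
| 5% | 0.5 | 1.004 | 2.0% | 1.003 | 2.8% |
| 5% | 1 | 0.972 | 5.6% | 1.001 | 2.9% |
| 5% | 2 | 0.946 | 7.4% | 1.003 | 2.5% |
| 5% | 4 | 0.919 | 13.7% | 1.004 | 2.5% |
| 10% | 2 | 0.912 | 14.6% | 1.000 | 2.5% |
| 10% | 4 | 0.879 | 25.1% | 1.003 | 2.5% |

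The full set gave 0.998 to 1.003 throughout. With a true hazard ratio of 0.70, the one-arm rule gives 0.684 for early deaths only, 0.660 and 0.651 for 5% at two and four times the hazard, and 0.614 for 10% at four times. The two-arm rule gives 0.699 to 0.702. PFS, iPFS and the response endpoints were not simulated.

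**The case against.** The strongest reply is that no decision rests on this analysis. Every formal test uses all randomized subjects, Per Protocol p-values are descriptive, and a failed primary analysis cannot be rescued here. The false favourable rates above therefore describe a test that the plan does not use for inference. Nor is this the only check on bias: SAP Sections 10.5.4.1 and 10.5.4.2 add analyses of assessment timing, remote deaths, informative censoring, subsequent therapy and unblinding. All of this stands, and it limits the seriousness of the point. It does not make the definition sound.

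Second, the direction is expected rather than certain. Entry requires ECOG 0 or 1 and injectable disease, the first scheduled on-study tumor assessment is at week 12, and dosing continues to confirmed progression, so heavy drop-out for progression by week 3 is unlikely. Injections also stop when injectable lesions disappear, which is a favourable reason to miss one. This stands as a caveat. In the simulation the shift vanished only when those who missed a dose had a clearly better prognosis (half the hazard).

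Third, the size depends on the inputs. In a simpler exponential model with 1% to 3% missing a dose at one to two times the hazard, the hazard ratio is about 0.98 to 1.00. That leaves out deaths before week 3, which the rule necessarily removes; including them gives about 0.96 to 0.97.

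Fourth, a symmetric rule still conditions on a post-randomization event. The reasons for missing an injection may differ by arm: protocol Section 2.2 reports more chills, pyrexia and injection-site pain with talimogene laherparepvec than with GM-CSF. The value of 1.00 for the two-arm rule assumes that missing a dose is unrelated to arm. This stands, and it is why exclusions should also be reported by arm and reason.

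**Conclusion.** The concern holds. The asymmetry is explicit in SAP Section 7.7 and nothing elsewhere corrects it. The likely effect is a Per Protocol OS hazard ratio biased towards talimogene laherparepvec. With no true effect it is about 0.976 from early deaths alone, which rests only on the design's own survival curve. It is roughly 0.95 to 0.88 if 5% to 10% more miss a dose with two to four times the hazard, which rests on assumptions that the documents neither support nor exclude. The bias is confined to descriptive sensitivity analyses. The plan should be corrected because it relies on this set to detect bias, but the primary inference is not at risk.

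**What to change.** In SAP Section 7.7, make the dose rule symmetric: exclude subjects in either arm who did not receive the first two consecutive injections of talimogene laherparepvec or placebo. Add a table of Per Protocol exclusions by arm and reason, so that any remaining imbalance can be seen. Dropping the dose rule altogether would also remove the asymmetry.

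The cost is one sentence, one filter and one table. Across the simulated scenarios about 5 to 38 placebo subjects would leave the sensitivity analysis. Trial conduct, sample size, alpha and the primary analysis do not change.

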7.8 Retreatment Analysis Set

The retreatment analysis set will include subjects receiving second-course of treatment in retreatment phase. The option of retreatment is available only for subjects in phase 1b as documented in country-specific protocols.

7.9 Subgroup Analyses

Efficacy analyses specified for the Full Analysis Set for phase 3 will be repeated within the following subgroups:

- PD-L1 status (positive, not positive) at baseline
- Disease stage (less advanced [stage IIIB/C-IVM1a], more advanced [stage IVM1b/c]) at baseline (IVRS)
- Prior treatment with BRAF inhibitor (IVRS)
- Region, if applicable (USA or non-USA)
- Age: < 65, ≥ 65; < 75, ≥ 75 years
- LDH: ≤ ULN vs > ULN
- Sex (female vs male)
- ECOG performance status (0 vs 1)
- HSV-1 serostatus (positive vs negative vs missing/unknown)
- The sum of longest, or shortest for nodal, diameters of baseline target lesions (SLD) determined by BICR (**≤ median of SLD vs > median of SLD**)
- Baseline *BRAF*^{V600} mutation (yes vs no vs missing/unknown)

The sum of longest, or shortest for nodal, diameters of baseline target lesions (SLD) will be dichotomized into two groups based on the median calculated at the time of analysis.

[figure not shown]
These subgroups will be re-examined for appropriateness and may be re-categorized or omitted (due to small sample size, for example, if there are < 10% of subjects within a subgroup) before unblinding. The analyses of these subgroups will be exploratory in nature.

The treatment effects in subgroups will be estimated using stratified odds ratio for binary endpoints; and stratified HR for time to event endpoints. Stratification factors in the analysis model will include the randomization stratification factors as well as PD-L1 status at baseline (positive vs not positive). In the case of a subgroup analysis of one of the stratification factors, only the other two stratification factors will be included in the models. To evaluate the efficacy of talimogene laherparepvec in combination with pembrolizumab in subgroups defined by the stratification factors and key covariates, the treatment effect will be investigated using the Gail and Simon quantitative and qualitative interaction tests (1985). Post hoc power for a nominal 2-sided 5% significance level test

may be calculated to help aid in the assessment (see code fragment in [Appendix C](#)).

The adjusted hazard ratio of the treatment effect with the corresponding 95% confidence interval and p-value adjusting for each of the subgroup variables listed above, using the stratified Cox proportional hazards (PH) model, as well as adjusting for all subgroup variables simultaneously in a multiple regression analysis, will be presented.

Subgroup analysis of exposure by age (< 65 vs ≥ 65, < 75 vs ≥ 75 years), gender and race (white vs non-white) will be presented. Subgroup analysis of adverse events by age, gender, and race will also be presented.

8. Interim Analysis and Early Stopping Guidelines

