10.1.3 Covariates and Subgroups

Randomization will be stratified by stage of disease: less advanced stages (IIIB, IIIC, and IVM1a) versus more advanced stages (IVM1b and IVM1c) and by prior BRAF inhibitor therapy: no prior BRAF inhibitor versus prior BRAF inhibitor with or without MEK inhibitor.

[figure not shown]
The following baseline covariates and randomization stratification factors may be used to examine efficacy in subgroups or in multivariate analyses:

[figure not shown]
- Region, if applicable (USA or non-USA)
- Age: < 50, ≥ 50; < 65, ≥ 65; < 75, ≥ 75 years
- Individual disease stage: IIIB vs IIIC vs IVM1a vs IVM1b vs IVM1c
- Grouped disease stage: IIIB/C-IVM1a vs IVM1b/c (CRF and IVRS)
- Grouped disease stage: IIIB/C-IVM1b vs IVM1c
- LDH: ≤ ULN vs > ULN
- Sex (female vs male)
- ECOG performance status (0 vs 1)
- HSV-1 serostatus (positive vs negative)
- The sum of longest, or shortest for nodal, diameters of target lesions (SLD) **determined by blinded independent central review (will be dichotomized based on median)**
- **Baseline PD-L1 status (positive vs not positive)**
- Prior BRAF inhibitor (none vs BRAF inhibitor alone vs BRAF and MEK inhibitors in combination): if subjects included in each of the 2 BRAF related category represent ≥ 10% of the study population (CRF)
- Prior BRAF inhibitor (yes versus no BRAF inhibitor with or without MEK inhibitors) (IVRS)
- **Baseline of BRAF^{V600} mutation: yes vs no vs missing/unknown**

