10.5.2 Primary Endpoint

10.5.2.1 Phase 1b

Subject incidence of DLT: The subject incidence of DLT will be summarized using the DLT analysis set.

10.5.2.2 Phase 3

The primary analyses of the primary endpoints of PFS and OS will be based on stratified log-rank tests as a primary method for testing the null hypothesis of no treatment difference.

The stratification factors will include randomization factors per IVRS and PD-L1 status at baseline (positive vs not positive). Inclusion of PD-L1 is considered in the stratified analysis because PD-L1 overexpression could be a potential prognostic factor, and its pretreatment status may not be able to be confirmed prior for use as a stratification factor at the time of randomization. In order to allow for the use of PD-L1 status in a stratified analysis, indeterminate and missing PD-L1 status will be classified together with the “negative” PD-L1 group. Hazard ratios will be estimated using Cox proportional hazards (PH) models stratified by randomization factors per IVRS and the baseline

PD-L1 status (positive vs not positive). Kaplan-Meier (KM) time to event curves will be presented by the randomized treatment group.

Statistical testing of a treatment effect for PFS and OS will follow the multiple hypothesis testing procedure as described in [Section 10.5](#).

Subgroups and covariates for analyses of PFS and OS will include, but not limited to, disease stage (IIIB/C to IVM1a, IVM1b/c), known PD-L1 status (positive, negative) and prior treatment with BRAF inhibitor.

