10.5.1.1 Analyses of Primary Efficacy Endpoint(s)

The primary analyses of the dual primary endpoints of PFS and OS will be triggered when 407 PFS events and 346 OS events have occurred, respectively, as well as OS interim analysis at 282 events (including a futility analysis) **and at 315 events**. The final analysis will occur approximately 5 years (60 months) after the last subject has been enrolled in phase 3.

[figure not shown]
- The analyses of primary efficacy endpoints will be based on stratified log-rank tests as a primary method for testing the null hypothesis of no treatment difference.

In order to allow for the use of PD-L1 status in a stratified analysis, indeterminate and missing PD-L1 status will be classified together with the “negative” PD-L1 group and analyze in the categories of “positive” vs “not positive” PD-L1 group.

Hazard ratios and corresponding two-sided 95% CI will be estimated using Cox PH models stratified by randomization stratification factors per IVRS (disease stage [IIIB-IVM1a vs IVM1b/c] and prior BRAF inhibitor therapy [no vs yes]) and the baseline PD-L1 status (positive vs not positive). KM time to event curves will be presented by the randomized treatment group.

Multiple statistical hypothesis tests will be conducted which include testing for primary endpoints of PFS and OS and the 3 secondary endpoints (iCRR, iPFS, and OS in the subgroup excluding disease stage IVM1c) at multiple analysis time points. To control the study-level overall Type I error at an overall 2-sided 0.05 level, a graphic-based multiple testing procedure for group sequential tests for multiple endpoints will be utilized ([Maurer and Bretz, 2013](#)) (see code fragment in [Appendix C](#)). No updated information will be used when a hypothesis is re-tested at a later time point after its primary analysis. A hypothesis can be re- tested repeatedly with a different nominal level that is propagated from rejecting other hypothesis test(s). The following figure illustrates the **Maurer-Bretz** multiple testing procedure with initial 2-sided α allocation specified as a fraction used for each hypothesis test. Each hypothesis is represented by a circle. A 0 fraction in the circle indicates a hypothesis that is tested conditional on rejection of another hypothesis. The fractions in the square on the directed arrows connecting 2 hypotheses indicate the proportion of α propagated to the next hypothesis test(s) when the current hypothesis is rejected.

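### SAP 7.9 pools unknown with negative in the phase 3 PD-L1 efficacy subgroup, while the protocol asks for known status in one section and the pooled grouping in another

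*SAP*

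**What the plan says.** **SAP.** Section 7.9 lists, among the subgroups in which the phase 3 efficacy analyses are repeated, "PD-L1 status (positive, not positive) at baseline". The label not positive is explained in SAP 10.5.1.1, where the group that receives the unknowns is the negative one: "In order to allow for the use of PD-L1 status in a stratified analysis, indeterminate and missing PD-L1 status will be classified together with the". In the same 7.9 list another biomarker keeps its unknowns apart: "HSV-1 serostatus (positive vs negative vs missing/unknown"). Baseline BRAF V600 mutation is treated the same way. Section 7.9 also plans Gail and Simon interaction tests in subgroups formed by the stratification factors and key covariates, calls the subgroup analyses exploratory, and lets subgroups be re-categorized or dropped before unblinding. Section 7.4 defines a set of known negatives: "The PD-L1 negative analysis set will include all subjects that are PD-L1 negative prior to randomization (phase 3"), and 7.5 does the same for positives. Section 10.4 tabulates baseline PD-L1 at three levels. Section 11 declares no change from the protocol.

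**Protocol.** Section 10.5.2.2 gives the same reason for pooling unknowns with negatives: "In order to allow for the use of PD-L1 status in a stratified analysis, indeterminate and missing PD-L1 status will be classified together". It then names as a PFS and OS subgroup "known PD-L1 status (positive, negative) and prior treatment with BRAF inhibitor". Section 10.1.3, the covariate and subgroup list, instead has "Baseline PD-L1 status (positive vs not positive").

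**The concern.** A stratified test has to place every randomized subject in some stratum, so putting unknowns with negatives is a reasonable device there. A subgroup estimate has no such need. Once the pooled group is used as a subgroup, its hazard ratio describes a mixture: subjects known to be PD-L1 negative plus subjects whose status nobody knows, some of whom may be positive. If the treatment effect differs by PD-L1, the mixture pulls the not-positive estimate toward the positive one, and the interaction test is weakened in the same direction.

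Unknown status is foreseeable. Inclusion criterion 111 lets an otherwise eligible subject be enrolled after a repeat sample also proves unevaluable. Interest in PD-L1-negative disease is also visible in the documents: a phase 1b exploratory objective asks whether the virus changes PD-L1 expression in subjects whose tumours are negative beforehand, and Protocol 2.4 reports raised PD-L1 expression after treatment in phase 1b responders. At stake is whether the report can say anything specific about known PD-L1-negative subjects, and whether the SAP delivers what Protocol 10.5.2.2 lists.

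**Working it through.** No sample size, power or alpha figure is involved, so there is no plan figure to reproduce. The check is mainly a comparison of text.

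1. *Purpose of the pooling.* Protocol 10.5.2.2 and SAP 10.5.1.1 give one reason, use in a stratified analysis. Neither extends it to subgroup estimates.
2. *Subgroup definition.* Protocol 10.5.2.2: known status, two levels. Protocol 10.1.3, SAP 4.2 and SAP 7.9: positive versus not positive. The conflict therefore lies within the protocol, and the SAP has followed one side of it.
3. *Declaration.* SAP 11 lists no changes, so the departure from 10.5.2.2 is not recorded.
4. *Use of the known-negative set.* SAP 7.4 covers phase 3, but the only visible analysis naming the set is PD-L1 induction in phase 1b (SAP 10.5.3.1). The three-level table in SAP 10.4 is descriptive and carries no treatment effect.
5. *Interaction test.* PD-L1 enters as a stratification factor in its two-level form, so the Gail and Simon test as written would compare positive with the mixed group.

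**Illustration of size, all inputs assumed.** Let f be the share of events in the not-positive group that come from subjects of unknown status, and q the share of those that are truly positive. As an approximation,

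log HR(not positive) = (1 − fq) × log HR(negative) + fq × log HR(positive),

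and the log-HR contrast between the two reported groups shrinks by the fraction fq. Take f from 5% to 30% and q from 50% to 75%, so fq runs from 0.05 × 0.50 = 0.025 to 0.30 × 0.75 = 0.225.

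- HR 0.55 in negatives, 0.80 in positives. Low end: exp(0.975 ln 0.55 + 0.025 ln 0.80) = 0.555. High end: exp(0.775 ln 0.55 + 0.225 ln 0.80) = 0.598.
- HR 0.80 in negatives, 0.55 in positives: 0.793 to 0.735.
- HR 0.67 in both: 0.67 throughout.

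In the first two cases the contrast is attenuated by 2.5% to 22.5%. Harsher assumptions (f from 10% to 40%, q from 50% to 80%, HR 0.50 in negatives and 0.80 in positives) give fq from 0.05 to 0.32 and a not-positive HR of about 0.51 to 0.58.

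**The case against.** The strongest reply is that the SAP follows the protocol's own subgroup list. Protocol 10.1.3 is headed Covariates and Subgroups and reads positive versus not positive, and the Amendment 5 change log shows that this wording deliberately replaced a three-level item. The SAP is written to Amendment 5. This stands in part: a reader might infer that the SAP breaks a single clear protocol instruction, and the documents do not support that. But 10.5.2.2 is also current text, it is the passage specific to PFS and OS, and the SAP neither implements it nor mentions the choice.

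A reader might also infer that the trial will never report the effect in PD-L1-negative subjects. That goes too far. Protocol 10.5.2.2 still calls for the known-status subgroup, SAP 7.4 and 7.5 define the phase 3 sets, and 7.9 permits re-categorization before unblinding. The visible SAP also skips from 10.5.3.1 to 10.5.3.3, and some content is redacted or placed in supplemental plans. The claim must be limited to what the visible text assigns. Permission to re-categorize is still not a commitment to do so.

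Other points stand as limits on importance. The subgroups are exploratory. The protocol brings PD-L1 into phase 3 as a possible prognostic factor, and no visible phase 3 objective concerns PD-L1-negative disease. SAP 10.1 counts any available positive result as positive, which reduces the number of hidden positives among the unknowns. The HSV-1 comparison is not uniform, since SAP 4.2 lists only two levels for it. Finally, matching the subgroup to the stratum is tidy, but a known-negative subgroup can equally be stratified by the other two factors, as 7.9 prescribes.

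**Conclusion.** The point holds as an undeclared mismatch in an exploratory analysis. SAP 7.9 applies to subgroup estimates a pooling justified only for stratification; Protocol 10.5.2.2 and 10.1.3 disagree; the SAP follows 10.1.3 without noting the difference; and no visible phase 3 efficacy analysis is assigned to known PD-L1-negative subjects.

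The primary stratified tests, alpha and power are not affected, and any inference that the pooling biases them is unsupported. The numerical effect on the subgroup result cannot be established from the documents, because they give no rate of indeterminate or missing PD-L1. It is zero if the treatment effect does not differ by PD-L1, small if few subjects are unknown, and grows with both the unknown share and the true difference. The hazard ratios above are illustrations only. The change is worth making because it is cheap and settles a conflict between current protocol passages before unblinding.

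**What to change.** - In SAP 7.9, and in the matching covariate line of 4.2, report PFS and OS subgroup estimates for known PD-L1 positive and known PD-L1 negative. The 7.4 and 7.5 sets may be used. Those sets rest on status before randomization while SAP 10.1 counts any positive result whatever its timing, so say which rule governs.
- Show indeterminate or missing as its own level, as 7.9 already does for HSV-1 and BRAF V600, unless too few subjects fall in it.
- Run the Gail and Simon PD-L1 interaction test on known positive versus known negative.
- Keep positive versus not positive as the stratification factor in the primary and other stratified analyses.
- Reconcile Protocol 10.1.3 with 10.5.2.2. If the pooled grouping is retained as the only subgroup, record the difference from 10.5.2.2 in SAP 11.

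Cost: wording changes and one more row in the subgroup display. No new data are needed, since the three-level variable is already tabulated under SAP 10.4. The negative subgroup becomes smaller by the number of subjects of unknown status, which is a real loss of precision if that number is large.
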